Serious Health Threat (ISO 14155: 2020 3.46)	A signal from any adverse event or device deficiency that indicates an imminent risk of death or a serious deterioration in the health in subjects, users or other persons, and that requires prompt remedial action for other subjects, users or other persons. Note: This would include events that are of significant and unexpected nature such that they become alarming as a potential serious health hazard or possibility of

Unavoidable events are conditions which do not fulfill the definition of an Adverse Event, such as those medical occurrences, clinical signs (including abnormal laboratory findings), diseases or injuries that are not untoward in nature, specifically, those resulting from the intended injury such as the index procedure. The events listed in [Table 11-2](#) are expected for patients undergoing the Index Procedure, and do not need to be reported as an AE unless they occur outside of the stated timeframe, are otherwise considered to be an AE according to the treating investigator or are suspected or confirmed to be device-related.

*Medtronic Business Restricted*

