**Table 11-2: Non-Reportable Medical Occurrences Associated with the Index Procedure**

Event	Timeframe (hours) from the Index Procedure
Short transient episode of arrhythmias or conduction disturbances (including ventricular fibrillation) during index procedure	0
Confusion, anxiety and/or disorientation (other than TIA/stroke) starting within 48 hours with or without medical intervention	120 (5 days)
Temporary change in mental status (other than TIA/stroke) not requiring additional medical interventions or new medical assessments (eg, CT)	72
Dizziness and/or lightheadedness with or without treatment	24
Headache with or without treatment	72
Sleep problems or insomnia with or without treatment	120 (5 days)
Mild dyspnea or cough with or without treatment	72
Oxygen supply after extubation / “forced breathing therapy”	48
Diarrhea with or without treatment	48
Obstipation / Constipation with or without treatment	72
Anesthesia-related nausea and/or vomiting with or without treatment	24
Low-grade fever (<101.3°F or <38.5°C) without confirmed infection	48
Low body temperature	6
Pain (eg, back, shoulder) related to laying on the procedure table with or without treatment	72
Incisional pain (pain at access site) with or without standard treatment and patient not returning to clinic to have additional treatment	No time limit
Pain in throat and/or trachea due to intubation	72
Stress hyperglycemia	72
Mild to moderate bruising or ecchymosis	168 (7 days)
Atelectasis / Pleural Effusion not requiring punctuation	168 (7 days)
Edema resulting in weight increase up to 4 kg / 9lbs from baseline	68 (7 days)

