## 17.1.22 ENCEPHALOPATHY

Altered mental state (e.g., seizures, delirium, confusion, hallucinations, dementia, coma, psychiatric episode, etc.).

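### Table 11-2 of the early feasibility CIP gives edema two different non-reportable limits in one cell, and its two mental-status rows overlap with no rule on which governs

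*Combined protocol and SAP*

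**What the plan says.** Section 11.4 of the early feasibility study CIP (Version 4.0) introduces Table 11-2 as a list of occurrences expected after the index procedure. They "do not need to be reported as an AE unless they occur outside of the stated timeframe", or unless they "are otherwise considered to be an AE according to the treating investigator or are suspected or confirmed to be device-related". The limits stand in a column headed "Timeframe (hours) from the Index Procedure".

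Three rows matter here:

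- "Confusion, anxiety and/or disorientation (other than TIA/stroke) starting within 48 hours with or without medical intervention": limit 120 hours, glossed as 5 days.
- "Temporary change in mental status (other than TIA/stroke) not requiring additional medical interventions or new medical assessments (eg, CT": limit 72 hours.
- "Edema resulting in weight increase up to 4 kg / 9lbs from baseline": limit 68 hours, glossed as 7 days.

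The two rows directly above edema (bruising; atelectasis or pleural effusion) print 168 hours for 7 days. Section 17.1.22 defines encephalopathy as "Altered mental state (e.g., seizures, delirium, confusion, hallucinations, dementia, coma, psychiatric episode, etc", so the CIP itself counts confusion among altered mental states. Neither Section 11.4 nor the table says what to do when an episode fits more than one row.

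**The concern.** These limits are operative. They decide whether a site opens an adverse event form at all, and sponsor and CEC review under Sections 11.5.2 and 12.1 works from what sites report. A cell whose hours and days disagree cannot be applied consistently. Nor can two overlapping rows that treat intervention in opposite ways: one disregards it, while the other makes it disqualifying.

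The primary objective (Section 4.1.1) is descriptive and concerns the nature, severity and frequency of complications. Uneven capture between sites therefore bears on the quantity the study sets out to describe. A smaller question is whether a serious event could go unreported under one of these rows and so miss the primary safety endpoint in Section 4.2.1.

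**Working it through.** **Step 1: hours against days.** The formula is hours = days × 24, applied to the three hour/day pairs in Table 11-2.

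- 120 h with 5 days: 5 × 24 = 120. Agrees.
- 168 h with 7 days: 7 × 24 = 168. Agrees.
- 68 h with 7 days (edema): 7 × 24 = 168, and 68 / 24 = 2.83 days. Does not agree.

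The edema gap is 168 − 68 = 100 h, or 100 / 24 = 4.17 days. It is the same whether the timeframe means onset or persistence.

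**Step 2: the two mental-status rows as rules.** Times are hours from the index procedure, and the timeframe is first taken to mean persistence.

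- Row A (confusion): exempt if onset ≤ 48 and last present ≤ 120, with or without intervention. The row is silent on new assessments, so imaging is not treated as disqualifying.
- Row B (mental-status change): exempt if there was no intervention or new assessment and last present ≤ 72. There is no onset limit.

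| Episode | Onset | Present to | Intervention or assessment | Row A | Row B |
|---|---|---|---|---|---|
| 1 | 24 | 60 | no | exempt | exempt |
| 2 | 24 | 100 | no | exempt | not exempt |
| 3 | 24 | 60 | yes | exempt | not exempt |
| 4 | 24 | 100 | yes | exempt | not exempt |
| 5 | 60 | 70 | no | not exempt | exempt |
| 6 | 60 | 70 | yes | not exempt | not exempt |
| 7 | 60 | 100 | no | not exempt | not exempt |
| 8 | 24 | 130 | no | not exempt | not exempt |

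Episodes 2 to 5 get a different answer according to the row a site consults. They represent three classes:

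- untreated confusion starting by 48 h and still present at 72 to 120 h;
- confusion starting by 48 h that needs intervention or imaging;
- untreated confusion starting at 48 to 72 h.

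**Step 3: does precedence matter?** If satisfying any one row is enough, episodes 1 to 5 are all exempt and nothing conflicts. If a site must satisfy both rows, only episode 1 is exempt. The CIP does not choose between these.

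**Step 4: onset or persistence.** In Row A, reading 120 h as an onset limit would make it redundant, since onset is already capped at 48 h; persistence is the likelier meaning there. Row B gives no such clue. If its 72 h means onset while Row A keeps persistence, episode 2 becomes exempt under both rows, and episodes 7 and 8 become exempt under Row B only. The disputed set changes but does not disappear.

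**Step 5: route to the primary endpoint.** Section 11.4 restores reporting on three triggers: outside the timeframe, investigator judgement, and suspected or confirmed device-relatedness. Table 11-1 makes an event serious if, among other things, it prolongs hospitalization. Table 11-4 has causality judged against the procedure as well as the device components. Neither seriousness nor procedure-relatedness is a trigger. Treated confusion that starts by 48 h, ends by 120 h, lengthens the stay and is attributed to the procedure alone therefore fits Row A, and reporting it rests on the investigator's judgement.

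**The case against.** The strongest reply is that Table 11-2 is a list of exemptions, and on the natural reading one satisfied row is enough. The rows name different occurrences with different qualifiers. An episode that needs a CT falls outside Row B, but Row B does not thereby make it reportable. Section 17.1.22 defines encephalopathy, not the wording of Table 11-2. This largely stands. A reader might infer that the CIP sets two incompatible windows for one event; the documents do not support that. They show an overlap without a precedence rule.

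A reader might also infer that every treated or imaged episode up to 120 h is in dispute. That drops Row A's onset condition: episode 6 is exempt under neither row, so its status is not in doubt.

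On edema, the conflict lies inside one cell, not between two entries. A dropped digit is the likely cause, either in the CIP or in its conversion to text, and the 7-day gloss still gives sites a limit. That is a good reason to check the page first. It does not reconcile the two figures as they stand.

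Finally, Section 11.4 presents the list as conditions that are not adverse events, and it restores reporting for device-related suspicion and on investigator judgement. Both mental-status rows exclude TIA and stroke, and Section 9.12 requires follow-up of suspected ones. These safeguards are real and cover much of the route to the endpoint. They leave open the gap in Step 5.

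**Conclusion.** The edema cell is wrong as written: its two figures differ by 100 h (4.17 days), and edema between 68 h and 168 h is reportable on one and exempt on the other. This assumes only that the text matches the printed page.

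The mental-status rows overlap, and the three classes in Step 2 can be classified differently by site. That rests on confusion counting as a change in mental status, on the persistence reading, and on the absence of a precedence rule. Under an any-row reading, the inconsistency arises only if sites do not all read the table that way.

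The main consequence is uneven counts of non-serious adverse events. The route to the primary endpoint is narrow. A reader might put its size at 1/45 = 2.2 percentage points per subject, from the enrollment cap in Section 8.1. The division is correct, but nothing in the documents shows that any subject's endpoint status would change, and they give no frequency for such events. With no pass criteria (Section 13.1), no decision threshold is affected either.

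**What to change.** 1. Check the printed page of the CIP, then reconcile the hour and day figures for edema so that the cell states one limit.
2. Reconcile the two mental-status rows: state which governs when an episode fits both, and whether the timeframes in Table 11-2 refer to onset or to persistence. Which limit applies is for the sponsor to decide.
3. Add to Section 11.4 that an event meeting the SAE definition in Table 11-1 is reportable regardless of Table 11-2.

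The cost is a CIP table correction, handled under Section 15.7 with IRB and regulatory approval as applicable, a memo to sites, and a few more adverse event forms.

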## 11.5 Reporting of Adverse Events

Adverse events and device deficiencies that occur during this trial are required to be reported to Medtronic via the AE or Device Deficiency CRF, as soon as possible after the event occurs, but no later than the timeframes listed in [Table 11-3](#) or local requirements, whichever is more stringent.

*Medtronic Business Restricted*

**CONFIDENTIAL**

056-F275, vC Clinical Investigation Plan Template

# The Early Feasibility Study of the Intrepid™ TMVR Transseptal System Clinical Investigation Plan

Version 4.0

Page 52 of 102

Medtronic

Investigators are obligated to report adverse events in accordance with the requirements of their reviewing IRB and local regulations.

The Sponsor is obligated to report adverse events and device deficiencies that occur during this trial to the Regulatory Authorities and IRB/EC as per local requirements.

**Table 11-3: Adverse Event Reporting Timelines [Investigator to Sponsor]**

Event Type	Timeframe for Reporting
Adverse Event (AE)	Recommended within 10 working days of the investigator's / site's first knowledge of the event
Serious Adverse Event (SAE)	Immediately, but no later than three (3) working days of the investigator's / site's first knowledge of the event
Adverse Device Effect (ADE) or Device Related Adverse Event	Immediately, but no later than three (3) working days of the investigator's / site's first knowledge of the event
Serious Adverse Device Effect (SADE)	Immediately, but no later than three (3) working days of the investigator's / site's first knowledge of the event
Unanticipated Adverse Device Effect (UADE)	Immediately, but no later than three (3) working days of the investigator's / site's first knowledge of the event
Unanticipated Serious Adverse Device Effect (USADE)	Immediately, but no later than three (3) working days of the investigator's / site's first knowledge of the event
Device Deficiency	Immediately, but no later than three (3) working days of the investigator's / site's first knowledge of the event
Device Deficiency that might have led to a SADE	Immediately, but no later than three (3) working days of the investigator's / site's first knowledge of the event
Mandatory Problem Reporting Incident (Canada ONLY)	Immediately, but no later than three (3) working days of the investigator's / site's first knowledge of the event

## 11.5.1 Emergency Contact Details for Reporting SAE, SADE, U(S)ADE, and Device Deficiencies

Investigators should contact their designated Medtronic representative or clinical trial monitor immediately if they have any questions regarding reportable AEs. Medtronic will provide sites

*Medtronic Business Restricted*

**CONFIDENTIAL**

056-F275, vC Clinical Investigation Plan Template

# The Early Feasibility Study of the Intrepid™ TMVR Transseptal System Clinical Investigation Plan

Version 4.0

Page 53 of 102

Medtronic

with a copy and maintain a listing of current sponsor contact details, inclusive of safety reporting.

## 11.5.2 Adverse Event and Device Deficiency Classification

All AEs and DDs will be reviewed by a Medtronic representative. AEs will be classified according to the definitions provided.

Upon receipt of AE at Medtronic, a Medtronic representative will review the AE/DD for completeness and accuracy and when necessary will request clarification and/or additional information from the Investigator. Source documents to support adjudication may be requested. Medtronic will utilize MedDRA for Regulatory Activities, to assign a MedDRA term for each AE based on the information provided by the investigator.

Regulatory reporting of AEs and DDs will be completed according to local regulatory requirements. Refer to [Table 11-4](#) for a list of required investigator and Medtronic reporting requirements and timeframes. It is the responsibility of both to abide by any additional AE reporting requirements stipulated by the IRB responsible for oversight of the study.

For emergency contact regarding a UADE, USADE, SAE and/or SADE, contact a study representative

immediately (refer to the study contact list provided in the study site's study documents binder).

AEs and Deaths will be classified according to the standard definitions as outlined below:

**Table 11-4: Adverse Event Classification Responsibilities**

What is classified?	Who classifies?	Classification Parameters
Relatedness	Investigator	Classifying causal relationships between the event and the Intrepid™ TMVR bioprosthetic (TMVR), delivery catheter system (DCS), Loading System, and the TMVR procedure.
	Sponsor	Classifying causal relationships between the event and the Intrepid™ TMVR bioprosthetic (TMVR), delivery catheter system (DCS), Loading System and the TMVR procedure.
Seriousness	Investigator	SAE, DD with SADE potential
	Sponsor	SAE, UADE/USADE (for all system or procedure related adverse events), DD with SADE potential
Diagnosis	Investigator	Based on presenting signs and symptoms and other supporting data
	Sponsor	MedDRA term assigned based on the data provided by Investigator

*Medtronic Business Restricted*

**CONFIDENTIAL**

056-F275, vC Clinical Investigation Plan Template

### **11.5.3 Adverse Event and Device Deficiency Reporting Requirements**

Regulatory reporting of AEs and DDs will be recorded and reported according to local regulatory requirements. It is the responsibility of the Investigator and the sponsor to abide by the AE reporting requirements stipulated by local law and the study site's IRB. Refer to [section 15.8.1](#) and [section 15.8.2](#) for reporting requirement.

## **11.6 Subject Death**

All subject deaths must be reported by the investigator to Medtronic on an AE form (AE with outcome of death) as soon as possible after the investigator first learns of the death. In case of death, there should be one AE with the outcome of death.

In the event of a subject's death, it is recommended that the implanted system be explanted and returned to Medtronic for analysis whenever possible per local process. Local laws and procedures must be followed where applicable. If any system component is returned to Medtronic, internal return product reporting systems may be used to gather additional information about the returned device/component.

A copy of the death certificate, if available and allowed by state/local law, should be sent to the Medtronic clinical study team. When a death occurs in a hospital, a copy of the death summary report and all relevant hospital records, if available should be sent to the Medtronic clinical study team. If an autopsy is conducted, a copy of the autopsy report should also be sent to the Medtronic clinical study team if available and allowed by state/local law. When the death occurs at a remote study site, it is the investigative study site's responsibility to attempt retrieval of information about the death. Additionally, device disposition information should be updated.

In summary, the following data will be collected:

- Date of death
- Detailed description of death
- Cause of death
- Relatedness to system and/or procedure
- Device disposition information
- Death summary/hospital records (if available and allowed by state/local law)
- Autopsy report (if available and allowed by state/local law)
- Death certificate (if available and allowed by state/local law)

### **11.6.1 Death Classification and Reporting**

Sufficient information will be required in order to properly classify the subject's death.

For all deaths, investigators must assess and document the following information on the Study Exit CRF.

*Medtronic Business Restricted*

**CONFIDENTIAL**

056-F275, vC Clinical Investigation Plan Template

# The Early Feasibility Study of the Intrepid™ TMVR Transseptal System Clinical Investigation Plan

Version 4.0

Page 55 of 102

Medtronic

- Date of death
- Primary death category

**Table 11-5: Subject Death Classification Responsibilities**

What is classified?	Who classifies?	Classification Parameters
Relatedness	Investigator	Classifying causal relationships between the event and the Intrepid™ TMVR bioprosthesis (TMVR), delivery catheter system (DCS), loading system, and the TMVR procedure.
Death Classification	Investigator	Sudden Cardiac, Non-sudden Cardiac, Non-cardiac, Unknown

The CEC will review deaths and provide a final adjudication of the primary cause of death and classification of death.

Regulatory reporting of Subject Deaths will be completed according to local regulatory requirements.

*Medtronic Business Restricted*

**CONFIDENTIAL**

056-F275, vC Clinical Investigation Plan Template

## 12.0 Data Review Committees

### 12.1 Clinical Events Committee Review

An independent Clinical Events Committee (CEC) will review and adjudicate, at a minimum, all deaths and primary endpoint related adverse events. The CEC will consist of, at a minimum: an interventional cardiologist, a cardiothoracic surgeon, an echocardiologist and a heart failure specialist who are not participants in the trial. Additional specialists, such as neurologists, may also be selected as part of the CEC.

The purpose of the CEC is to conduct a medical review and classify/adjudicate, at a minimum, all deaths and/or clinical endpoints collected in the trial according to definitions and processes outlined in the trial protocol and the CEC charter, which will be developed and approved by Medtronic and the CEC members. Safety endpoint results will be based on CEC adjudication.

All applicable events will be reviewed and adjudicated by a minimum of three CEC members. All other events will be reviewed and assessed by qualified internal Medtronic safety individual(s) to ensure that adjudication by the CEC is not required and that the events are appropriately classified by the investigator.

Prior to event adjudication, the CEC will draft a charter, in collaboration with Medtronic, to establish explicit rules outlining the minimum amount of data required and the algorithm followed in order to classify/adjudicate a trial endpoint related clinical event. CEC decisions will be documented in meeting minutes, which will be maintained in the trial master file and adjudication results will be recorded in the trial database.

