### **4.2 Study Endpoints**

#### **4.2.1 Primary Safety Endpoint**

The primary safety endpoint is implant, delivery or device related serious adverse events (through 30 days post-procedure).

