## **5.0 Study Design**

The Early Feasibility Study of the Intrepid™ TMVR Transseptal System is designed as a multi-center, prospective, non-randomized, investigational, early feasibility study to evaluate the safety and performance of transcatheter mitral valve replacement in patients with moderate-severe or severe, symptomatic mitral regurgitation who are deemed ineligible for conventional mitral valve surgery by the heart team. Subjects will be followed 5 years post-implant. The study methods include the following measures to minimize potential sources of bias:

- An external, independent Clinical Events Committee (CEC) will review and adjudicate, at minimum, all deaths and endpoint related adverse events. Safety endpoint results will be based on CEC adjudications.
- All sites will follow a standardized protocol for acquisition of echocardiographic endpoint data.
- Core labs will evaluate all echocardiograms. Echocardiographic trial endpoint results will be based on Core Lab assessments.
- Subjects will be screened to confirm eligibility for enrollment with pre-defined inclusion and exclusion criteria.

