## 5.3 Clinical Events Committee and Data Safety Monitoring Board

The combined Clinical Events Committee (CEC) and Data Safety Monitoring Board (DSMB) will provide independent medical review and adjudication of adverse event data used in the safety assessment of the investigational device. The CEC will adjudicate all deaths, serious adverse events (SAEs), and safety endpoint events reported by the investigators. The CEC will follow the recommendations of the Mitral Valve Academic Research Consortium (MVARC) for classifying adverse events that relate to clinical safety endpoints.

A DSMB will assess interim study data and provide recommendations to Medtronic regarding study conduct, should they identify any issues that may affect the safety of the study subjects. The DSMB consists of a minimum of three members: 1) cardiologist with expertise in the management of mitral disease, 2) a cardiothoracic surgeon with expertise in mitral valve repair and replacement, and 3) a biostatistician. DSMB members are free from bias towards the study and independent from both the study and investigators and Medtronic.

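### In the EFS, a non-fatal SAE that the investigator calls unrelated has no guaranteed route to independent adjudication of relatedness, although relatedness defines the primary safety endpoint

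*Combined protocol and SAP*

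**What the plan says.** Section 4.2.1 of the EFS CIP makes relatedness part of the primary endpoint. An SAE counts only if it is related to the implant, its delivery or the device, through 30 days.

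Section 5.0 lists independent adjudication among the measures against bias. The CEC "will review and adjudicate, at minimum, all deaths and endpoint related adverse events", and "Safety endpoint results will be based on CEC adjudications". Section 12.1 gives nearly the same scope: the CEC "will review and adjudicate, at a minimum, all deaths and primary endpoint related adverse events". The remainder goes to the sponsor's internal safety staff, who assess it "to ensure that adjudication by the CEC is not required and that the events are appropriately classified by the investigator".

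Table 11-4 assigns the classification of relatedness to the investigator and the sponsor, and has no CEC row. Table 11-5 gives relatedness of deaths to the investigator; the text below it has the CEC settle the cause and class of death.

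The only SAP in the file belongs to the transapical Pilot Study. Its section 5.3 is wider: "The CEC will adjudicate all deaths, serious adverse events (SAEs), and safety endpoint events reported by the investigators". Section 7.10 of that SAP repeats this scope.

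**The concern.** For a non-fatal SAE, the judgement that makes it an endpoint event is whether it is related. If the guaranteed CEC scope consists of events already judged related, that judgement comes before the CEC is involved and is made by the site and the device's manufacturer in an open study.

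The two kinds of error are then treated differently. An SAE called related goes to the CEC, which can overrule the call. An SAE called unrelated by both site and sponsor has no assured independent look at that call. The borderline is a matter of judgement: in 17.1.45, unlikely and possible differ by whether another cause is more likely, or only equally or less likely. What is at stake is the credibility of the study's main descriptive result, the frequency of related SAEs.

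**Working it through.** There is no stated figure to reproduce. The EFS has no hypothesis test, no power calculation and no statistically derived sample size (13.0). The check is mainly textual.

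**Routes to the CEC for an SAE through day 30**

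| Event | Route in the EFS CIP | Guaranteed? |
|---|---|---|
| Death | 5.0, 12.1 | Yes, whatever its relatedness |
| Non-fatal SAE called related | 5.0, 12.1 | Yes |
| Peak LVOT velocity of 2.7 m/s or more, or an AE/SAE tied to a rise in LVOT gradient during the procedure | 17.1.27 | Yes, without a device-relatedness call |
| Heart failure hospitalisation | 17.1.25, definition footnote | Expected by the adopted definition |
| Other non-fatal SAE called unrelated by the investigator | 12.1, sponsor screen | Only if sponsor staff refer it |

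The last row would include a bleed, stroke, kidney injury or arrhythmia called unrelated. The CIP describes no sample check of such events by the CEC.

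**Direction.** If an event in the last row is truly unrelated, nothing is lost. If it is truly related and not referred, the event count falls by one. The subject-level proportion falls too if the subject has no other qualifying SAE. Neither can rise by this path.

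**Illustration of size.** Every input except N = 45 (the EFS maximum, 8.2) is an assumption:

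- p: true share of subjects with a related SAE through 30 days
- m: share of those subjects whose only qualifying SAE the site calls unrelated
- c: share of these that the sponsor screen refers to the CEC
- d: share that are fatal and so reach the CEC anyway

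Expected reported rate = p × [1 − m(1 − c)(1 − d)]. Expected subjects missed = 45 × p × m(1 − c)(1 − d).

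With p = 0.30, m = 0.20 and d = 0:

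| c | Subjects missed | Reported rate |
|---|---|---|
| 0 | 45 × 0.30 × 0.20 = 2.7 | 24% |
| 0.5 | 45 × 0.30 × 0.20 × 0.5 = 1.35 | 27% |
| 1 | 0 | 30% |

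The range for p from 0.20 to 0.40, m from 0.10 to 0.30, c from 0 to 0.5 and d from 0 to 0.2 is:

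- smallest: 45 × 0.20 × 0.10 × 0.5 × 0.8 = 0.36 subjects
- largest: 45 × 0.40 × 0.30 × 1 × 1 = 5.4 subjects

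One subject is 1/45 = 2.2 percentage points. For scale, the exact 95% interval is 18.2% to 46.6% for 14/45 (31.1%), and 12.9% to 39.5% for 11/45 (24.4%). A three-subject shift lies well inside the sampling uncertainty, but it is a shift in one direction that the interval does not reflect.

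The model assumes that the CEC judges correctly whatever reaches it, and it ignores the LVOT and heart failure routes, which would reduce the number missed. If the CEC adjudicated every SAE through day 30, the term m(1 − c)(1 − d) would be zero. Errors by the CEC itself would remain.

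**The case against.** A reader might infer that the CEC never sees an SAE called unrelated, that such events get no independent review, or that errors are corrected only downwards. The documents support none of these.

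- **Other routes exist.** Deaths and the LVOT cases reach the CEC regardless of relatedness to the device, and the heart failure definition expects CEC adjudication.
- **The DMC is independent and reviews all SAEs and deaths (12.3).** That protects subjects. It does not close this gap, because the DMC is given no task of classifying relatedness and the endpoint result comes from the CEC.
- **The sponsor screen can correct upwards.** It checks the investigator's classification, and Table 11-4 has the sponsor judge relatedness too. The gap needs an error that passes both. What is missing is an independent guarantee, not every means of correction.
- **The scope is a minimum.** Section 12.1 also describes the CEC's task as covering the trial's clinical endpoints, and 5.0 omits the word primary. The phrase about events related to the primary endpoint is not defined operationally and could cover any SAE that bears on it. The charter may settle this, but it was not supplied, and the CIP itself promises no more.
- **The Pilot Study is not a clean benchmark.** Pilot SAP 5.3 and 7.10 have the CEC adjudicate all SAEs, but 7.9.1 says only that AEs may be adjudicated and otherwise uses the site's classification.
- **The study is descriptive.** No success criterion turns on the rate, and FDA receives event summaries for all subjects (13.0, 13.1). This limits the consequence. It does not remove it, because the descriptive rate is the primary result.

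**Conclusion.** The concern holds in a limited form. The EFS CIP guarantees CEC review of SAEs called related, but not of non-fatal SAEs called unrelated. Outside the specified cases, those depend on referral by sponsor staff. Any related event lost there lowers the reported rate.

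This rests on reading the guaranteed scope as events already classified as related, and on the CIP alone; a wider charter would narrow or close the gap. The size cannot be computed from the documents. The span of 0.36 to 5.4 subjects among 45 reflects chosen inputs and is not an estimate. Nothing in the documents shows that any event has been misclassified, and no sample size or power figure is affected.

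**What to change.** In EFS CIP 12.1, require the CEC to adjudicate both seriousness and relatedness of every SAE with onset through 30 days post-procedure, whatever the investigator or sponsor concluded. This is the scope stated in Pilot SAP 5.3 and 7.10. Keep sponsor triage for non-serious and later events. Make the same change to the scope in 5.0, add the CEC to the relatedness and seriousness rows of Table 11-4, and align the charter. If the charter already requires this, carrying its rule into 12.1 is enough.

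The cost is more cases for the existing committee, each needing at least three members under 12.1. The number of SAEs is not known in advance, but it is bounded by a 30-day window in at most 45 subjects. No new committee, visit or test is needed, and the sample size does not change. One limit remains: an event that site and sponsor both call non-serious would still depend on sponsor triage.
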